12.2 Best Corrected Visual Acuity

Best corrected visual acuity (BCVA) letter score will be measured at 4 meters using an Early Treatment Diabetic Retinopathy Study (ETDRS) chart. If the patient reads letters at 4 meters, the BCVA letter score will be 30 letters plus the 4 meter result. If the patient reads less than 20 letters at 4 meters, the letter score will be the sum of the 1-meter and 4-meter results. If the patient is unable to read letters at 1 and 4 meters then count fingers, hand motion, and light perception will be assessed. The Snellen equivalent to the letter score will also be collected. BCVA is measured at each visit.

For BCVA letter score, the observed and change from baseline will be summarized for each eye (study eye and fellow eye) using continuous descriptive statistics by visit for each treatment arm and for all patients. Counts and percentages of patients with a 15-letter loss will also be summarized for the change from baseline. A patient listing of BCVA will also be produced.

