5.2. Exclusion Criteria

Patients must NOT have met any of the following exclusion criteria to be included in the study:

1. Patients with 2 mm proptosis decrease between Screening and Day 1, or a 1-point decrease on the CAS 7-point scale between Screening and Day 1 and patients that no longer meet the eligibility criteria at the Day 1 ophthalmology assessment.
2. Patients with a known decreased best corrected visual acuity due to optic neuropathy as defined by a decrease in vision of 3 lines on the ETDRS chart (or equivalent), new visual field defect, or color defect secondary to optic nerve involvement within the last 6 months before Screening; or any known optic neuropathy or compression or any neurologic or neuro-ophthalmologic condition that may result in visual field loss.
3. Previous or any planned orbital irradiation/radiotherapy or planned orbital surgery for TED during the study period (ie, treatment and FU)
4. Any planned procedures or hospitalizations during the study. EXCEPTION: minor or routine procedures that do not interfere with the conduct of the study may be approved by the PI or designee

5. Poor peripheral venous access that would preclude study assessments
6. Use of oral and/or IV corticosteroid for conditions other than TED in the 6 weeks before Day 1 (topical steroids for conditions other than TED are allowed)
7. Active autoimmune disorder(s) requiring or likely to require treatment (other than Grave's disease and TED) that would interfere with study assessments, as determined by the PI or designee
8. Any liver function test result (including aspartate aminotransferase, alanine aminotransferase, gamma glutamyl transferase, or total bilirubin) $\geq 1.5 \times$ the upper limit of normal; levels may be repeated once at the discretion of the PI or designee during the Screening period or before dosing, and the lower of the 2 readings may be used (note that subjects with Gilbert's Syndrome will not be excluded)
9. Previous use of an anti-IGF-1R targeted treatment at any time.
 - a. 
10. Use of selenium within 3 weeks before Day 1 or expected use during the clinical trial (multivitamins that include selenium are allowed in usual doses)
11. Use or expected use of biotin (including multivitamins that include biotin) within 2 days before any laboratory collection
12. Receipt of blood products within 2 months before Day 1

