8.2.1. Best Corrected Visual Acuity, Visual Fields, and Color Defects

Change of best corrected visual acuity by ≥ 3 lines (15 words) at 4m on the ETDRS chart, new or increased visual field (by Humphrey field testing) or color defects (Ishihara test) may require additional assessments. If a different measure or assessment is used, it must be approved by the Medical Monitor and equivalent criteria used for assessment. Instructions will be provided in a study manual.

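### SAP 12.2 leaves out the lower limit on its first BCVA scoring rule, so an eye reading 1–19 letters at 4 m meets two rules that can give different scores

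*SAP*

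**What the plan says.** SAP 12.2 gives three scoring sentences in this order:

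- Rule 1: "If the patient reads letters at 4 meters, the BCVA letter score will be 30 letters plus the 4 meter result".
- Rule 2: "If the patient reads less than 20 letters at 4 meters, the letter score will be the sum of the 1-meter and 4-meter results".
- Fallback: "If the patient is unable to read letters at 1 and 4 meters then count fingers, hand motion, and light perception will be assessed".

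The score is then summarised by visit, as observed and as change from baseline, for the study eye and the fellow eye. The section adds: "Counts and percentages of patients with a 15-letter loss will also be summarized for the change from baseline". A patient listing of BCVA is also planned.

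Protocol 8.2.1 gives no scoring formula. It sets a three-line change at 4 m as something that "may require additional assessments", and leaves instructions to a study manual that is not among the documents.

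**The concern.** Rule 1 is triggered by reading letters at 4 m, with no minimum number. Rule 2 is triggered by reading fewer than 20. Both conditions are true for 1–19 letters, and no word such as "otherwise" or "except" says which prevails. The fallback applies only when no letters are read at either distance, so it does not settle the matter.

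The result can depend on how the text is coded. An if/else-if chain in the written order stops at rule 1. Two separate statements in the same order let rule 2 overwrite rule 1. The same data could then give different letter scores, different changes from baseline and, for some eyes, a different answer on the 15-letter loss. Change in ophthalmic assessments belongs to the primary safety objective, so the score should have one definition.

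**Working it through.** The documents state no figure for BCVA that could be reproduced, so the check compares the two rules directly.

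**Inputs**

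- L4 = letters read at 4 m; L1 = letters read at 1 m.
- Rule 1 (SAP 12.2): score = 30 + L4, for L4 ≥ 1.
- Rule 2 (SAP 12.2): score = L1 + L4, for L4 < 20.
- Loss flag (SAP 12.2): a 15-letter loss, read here as 15 or more.
- Assumption: L1 runs from 0 to 30. The documents give no maximum. The fixed credit in "30 letters plus the 4 meter result" suggests 30.

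**Overlap.** Both rules apply for L4 = 1 to 19. This needs no assumption.

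**Difference.** (30 + L4) − (L1 + L4) = 30 − L1.

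| L1 | Rule 1 minus rule 2 |
|---|---|
| 30 | 0 |
| 25 | 5 |
| 20 | 10 |
| 15 | 15 |
| 0 | 30 |

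If L1 could exceed 30, the sign would reverse: L1 = 40 gives −10.

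**When a loss is missed, baseline outside the overlap.** Let the baseline score be B = 30 + L4 with L4 ≥ 20, so B ≥ 50. Let the follow-up L4 be 1–19. Rule 1 gives a loss of B − 30 − L4, and rule 2 gives B − L1 − L4. Rule 1 misses a loss that rule 2 flags when the former is below 15 and the latter is 15 or more. The smallest loss rule 1 can give is B − 49, at L4 = 19. That is 14 at B = 63 and 15 at B = 64. A miss is therefore possible only for B = 50 to 63.

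| Baseline | Follow-up L4 / L1 | Loss, rule 1 | Loss, rule 2 |
|---|---|---|---|
| 50 | 10 / 20 | 50 − 40 = 10 | 50 − 30 = 20 |
| 52 | 12 / 20 | 52 − 42 = 10 | 52 − 32 = 20 |
| 55 | 15 / 20 | 55 − 45 = 10 | 55 − 35 = 20 |
| 63 | 19 / 29 | 63 − 49 = 14 | 63 − 48 = 15 |
| 64 | 19 / 29 | 64 − 49 = 15 | 64 − 48 = 16 |
| 80 | 10 / 20 | 80 − 40 = 40 | 80 − 30 = 50 |

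From 64 upward both rules flag the loss, but rule 1 understates it by 30 − L1.

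**Both visits in the overlap.** L4/L1 going from 15/30 to 8/18 gives 45 − 38 = 7 under rule 1 and 45 − 26 = 19 under rule 2.

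**Rules mixed across visits.** L4 = 15 and L1 = 12 at both visits, scored by rule 1 and then by rule 2, gives 45 − 27 = 18: a flagged loss with no change in vision.

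**Proposed wording.** With rule 1 limited to L4 ≥ 20, each eye meets exactly one rule. The eye with baseline 50 and follow-up 10/20 then scores 30, a loss of 20, and is flagged.

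**The case against.** The strongest reply is that the intended rule can be recovered from the text. If rule 1 took priority for 1–19 letters, rule 2 would be left with eyes reading nothing at 4 m, and its cut-off of 20 would do no work. Only the exception reading gives effect to both sentences. That stands, and it makes this a missing clause rather than two competing scoring methods. It does not close the gap, because the SAP states no precedence and the protocol supplies no formula.

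A reader might infer more than the documents support:

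- **That severe vision loss would generally go uncounted.** It would not. From a baseline of 64 or more, any fall into the 1–19 range is flagged by both rules. Protocol 5.1 requires disease that does not threaten sight, and Protocol 5.2 excludes "Patients with a known decreased best corrected visual acuity due to optic neuropathy". No minimum acuity is set, so low baselines from other causes remain possible, but nothing shows how many there are.
- **That rule 1 always overstates vision.** This holds only if L1 is below 30, and the direction rests on the assumed maximum of 30.
- **That the error is 12.5 percentage points.** With 8 patients planned per arm, 1/8 = 12.5% is the weight of any single event in any table. It does not measure this problem.

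It is also fair to note that in the example with baseline 52, the count at 4 m falls by only 10 letters (22 to 12). The other 10 letters of rule 2's 20-letter loss come from replacing the 30-letter credit at baseline with a measured 20 at 1 m.

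Finally, the BCVA summary carries no test, a listing is provided, and Protocol 8.2.1 states its trigger in chart lines rather than in the SAP score. Whether the score is derived in the eCRF, under the study manual or in analysis code cannot be seen from the documents, so no actual mis-scoring is shown.

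**Conclusion.** The point holds as a wording defect with a small consequence. That eyes reading 1–19 letters at 4 m meet both rules, and that the scores differ by 30 − L1, follows from SAP 12.2 alone. Overstatement under rule 1, by up to 30 letters, depends on L1 not exceeding 30. A missed 15-letter loss further requires a baseline score of 50–63 or both visits in the overlap range. Few eyes are likely to be affected. Only a descriptive safety summary is involved, and the primary efficacy analysis is untouched.

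**What to change.** In SAP 12.2, restrict the first scoring rule to eyes reading 20 or more letters at 4 m. This uses the SAP's own cut-off and makes the first two rules mutually exclusive. Then confirm that the score, whether derived in the eCRF or in the analysis program, uses this cut-off at every visit, so that baseline and follow-up are scored alike. The cost is one clause and one check of the derivation, with no new data.

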12.3 Visual Field

Visual field will be assessed using either a 10-2, 24-2, or 30-2 assessment as per the schedule of assessments. The results will be graded as normal, abnormal not clinically significant (NCS), or abnormal clinically significant (CS).

The visual field results data will be summarized by grade of normal, abnormal not clinically significant (NCS), or abnormal clinically significant (CS) for each treatment arm and for all patients at each visit for each eye (study eye and fellow eye). Percentages will be based on the number of patients in each treatment arm with normal, abnormal not clinically significant (NCS), or abnormal clinically significant (CS) responses. A patient listing of the visual field results will also be produced.

CONFIDENTIAL

The contents of this document are confidential to [REDACTED]
Unauthorized use, disclosure, or reproduction is strictly prohibited.

12.4 Ishihara Color Vision Test

Color vision will be assessed with the Ishihara Test which uses a series of multi-colored plates. Color vision will be assessed as per the schedule of assessments. The number of plates correct, and the total number of plates shown will be collected. A patient listing of the Ishihara Color Vision results will be produced.

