To assess the safety and tolerability of IV administration of LASN01 compared with placebo in patients with TED	
For randomized treatment arms:
 
 Treatment-emergent adverse events (TEAEs), changes in concomitant medications compared with placebo Changes from Baseline in clinical laboratory evaluations, vital signs, electrocardiograms, ophthalmic assessments, and physical

CONFIDENTIAL

The contents of this document are confidential to [REDACTED]
 Unauthorized use, disclosure, or reproduction is strictly prohibited.

	
examinations following study drug administration compared with placebo
 
For open-label treatment arm(s):
 
 • TEAEs, changes in concomitant medications • Changes from Baseline in clinical laboratory evaluations, vital signs, electrocardiograms, ophthalmic assessments, and physical examinations following study drug administration
Secondary: Pharmacokinetics	
To characterize the pharmacokinetic (PK) profile of IV administration of LASN01 in patients with TED	
For all treatment arms:
 
 • Serum LASN01 concentrations at specified time points
Exploratory: Immunogenicity	
Characterize the immunogenicity of IV administration of LASN01 in patients with TED	
For all treatment arms:
 
 • Incidences of antidrug antibodies at specified timepoints relative to Baseline
Exploratory: Pharmacodynamics	
To explore the potential pharmacodynamic profile of IV administration of LASN01 in patients with TED	
For all treatment arms:
 
 • Protein markers in blood relevant to the Interleukin-11 (IL-11) pathway

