6.3 Data Analysis Conventions

Ora will perform all data analyses described in this SAP using [REDACTED]. Outputs will be provided in RTF for tables and figures, and in PDF for tables, listings, and figures (TLFs) in landscape orientation. Each formal TLF deliverable will include three combined PDF files, one for each of the output types.

Data will be summarized and listed separately. Continuous variables will be summarized using the number of patients (n), mean, standard deviation (SD), median, minimum, and maximum. Additionally, coefficient of variation (CV%), geometric mean and geometric CV% will be provided for PK concentrations and parameters (except for T_{max}). Values of 0 will be considered missing when calculating the geometric means. Categorical data will present counts and percentages within each category. Standard Error (SE) may be added to continuous efficacy outputs for Total CAS. Individual patient data listings will also be produced. For all other parameters except for PK concentrations and PK parameters, minima and maxima will retain the same precision as raw values; means and medians will have one additional decimal place; SDs will have two additional decimal places. For PK concentrations and parameters except n, all other descriptive statistics will be presented with the same number of significant digits as raw PK concentrations (3 significant figures). Percentages will be rounded to one decimal place (e.g., XX.X%). Differences between active treatment and placebo will be calculated as Active – Placebo, and change from baseline as Follow-up Visit – Baseline.

Unless otherwise specified, all statistical tests will be one-sided at a significance level of $\alpha=0.1$. Confidence intervals (CIs) for differences between treatment arms will be two-sided at 95% confidence unless stated otherwise. All p-values will be rounded to four decimal places; p-values less than 0.001 will be shown as "<0.001," and those greater than 0.9999 as ">0.999."

Summaries will be presented by treatment arm, including 300 mg, 600 mg, pooled treatment group (300 mg and 600 mg) for efficacy, placebo arm, [REDACTED] and, where appropriate, by visit and eye (study eye and either eye). Where possible, p-values will be displayed for comparisons of relevant active treatment groups to placebo; [REDACTED]. Listings will be presented by patient number, treatment arm, visit, time point, and parameter as applicable based on enrolled patients unless otherwise specified.

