12.5 Slit Lamp Biomicroscopy

A slit lamp biomicroscopy examination of the cornea, conjunctiva, anterior chamber, iris, lens, eyelid, and pupil will be performed as per the schedule of assessments. The results will be graded as normal, abnormal NCS, or abnormal CS.

The results will be summarized using numbers and percentages for each treatment arm and for all patients at each visit for each eye (study eye and fellow eye). Percentages will be based on the number of patients in each treatment arm with responses and overall for all patients. Summary table will be presented for normal, abnormal NCS, or abnormal CS in cornea, conjunctiva, anterior chamber, iris, lens, eyelid, and pupil. A patient listing of the slit lamp biomicroscopy parameters will also be produced.

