12.7 Dilated Fundoscopy

A dilated fundoscopy examination of the vitreous, retina, macula, optic nerve, and choroid will be performed as per the schedule of assessments. The results will be graded as normal, abnormal NCS, or abnormal CS.

The results will be summarized using numbers and percentages for each treatment arm and for all patients for each eye (study eye and fellow eye). Percentages will be based on the number of patients in each treatment arm with responses. Summary table will be presented for normal, abnormal NCS, or abnormal CS in the vitreous, retina, macula, optic nerve, and choroid. A patient listing of the dilated fundoscopy parameters will also be produced.

CONFIDENTIAL

The contents of this document are confidential to [REDACTED]
Unauthorized use, disclosure, or reproduction is strictly prohibited.

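### Low-cost improvement: SAP Section 12 counts slit-lamp, visual-field and fundus grades only cross-sectionally and only lists Ishihara results, so none of these tests gets a by-arm summary of worsening from Baseline

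*SAP*

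**What the plan says.** - **Endpoint.** SAP Section 2, under primary safety, lists "Changes from Baseline in clinical laboratory evaluations, vital signs, electrocardiograms, ophthalmic assessments, and physical"; the last item is physical examinations, and for the randomised arms the comparison is with placebo. Protocol Section 3 has the same endpoint.
- **Slit lamp (SAP 12.5).** Each of seven structures gets one of three grades: normal, or abnormal without or with clinical significance. The planned table is described thus: "The results will be summarized using numbers and percentages for each treatment arm and for all patients at each visit for each eye". Both the study eye and the fellow eye are covered.
- **Visual field (SAP 12.3).** "The visual field results data will be summarized by grade of normal, abnormal not clinically significant (NCS), or abnormal clinically significant (CS"), again by arm, visit and eye.
- **Fundus (SAP 12.7).** "Summary table will be presented for normal, abnormal NCS, or abnormal CS in the vitreous, retina, macula, optic nerve, and choroid". The section gives arm and eye but does not mention visit. By-visit presentation follows from the general convention in SAP 6.3, "where appropriate, by visit and eye (study eye and either eye").
- **Colour vision (SAP 12.4).** "The number of plates correct, and the total number of plates shown will be collected". The only output is a listing: "A patient listing of the Ishihara Color Vision results will be produced".

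None of these four sections mentions Baseline, change, shift, or new or worsened findings. Each plans a listing, and SAP 6.3 says what listings carry: "Listings will be presented by patient number, treatment arm, visit, time point, and parameter as applicable".

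**The concern.** A count of abnormal eyes at a visit mixes findings present before the first dose with findings that arose afterwards. A change-from-Baseline endpoint asks about the second group, and protocol 8.2.1 treats new or increased field and colour defects as the event that may call for further assessment. As planned, a reader who wants the number of patients per arm who worsened must work through the listings by hand. For Ishihara there is also no pre-set rule for how large a fall in plates correct counts as worsening, so any threshold chosen later would be post hoc.

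Baseline abnormality is plausible, at least at the slit lamp. Entry requires a CAS of at least 4, and only two of the seven items are pain. So at least two lid, conjunctival or caruncle/plica signs must be present at entry. The documents do not say how these are graded at the slit lamp.

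**Working it through.** The plan states no figure on this point, so there is none to reproduce.

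**1. Which tests the endpoint clearly covers.** In the protocol 1.3 schedule, the footnote to the ophthalmic assessments row includes slit lamp, visual acuity and intraocular pressure. Visual fields, colour vision and dilated funduscopy have their own rows. Protocol 8.2 likewise names visual acuity, fields and colour defects first, and then separately lists change from Baseline in ophthalmic assessments. Slit lamp is therefore clearly inside the endpoint. The other three are inside only if the term is read broadly.

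**2. Numeric safety measures after Baseline in SAP Section 12.**

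| Measure | SAP section | Change from Baseline planned |
|---|---|---|
| BCVA letters | 12.2 | Yes, plus count with 15-letter loss |
| Ishihara plates | 12.4 | No, listing only |
| IOP | 12.6 | Yes |
| Weight | 12.9 | Yes |
| Vital signs | 12.10 | Yes |
| ECG intervals | 12.11 | Yes |
| Laboratory values | 12.12 | Yes |

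Six of the seven have it; Ishihara does not.

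**3. What cross-sectional counts leave open.** Let n be the eyes of one side in an arm, b the number abnormal at Baseline and f the number abnormal at a later visit. The number abnormal at both times lies between max(0, b + f − n) and min(b, f). Newly abnormal eyes therefore lie between f − min(b, f) and f − max(0, b + f − n). Here n = 8 is the planned arm size (protocol Table 2, SAP Table 1); b and f are assumptions for illustration.

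| b | f | Minimum new | Maximum new |
|---|---|---|---|
| 0 | f | f | f |
| 2 | 2 | 2 − 2 = 0 | 2 − 0 = 2 |
| 3 | 3 | 3 − 3 = 0 | 3 − 0 = 3 |
| 2 | 3 | 3 − 2 = 1 | 3 − 0 = 3 |

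If no eye is abnormal at Baseline, the count at a visit is exactly the number of new findings at that visit, and nothing is lost there. Otherwise the count gives only a range. Worsening within the abnormal grades is hidden in the same way: 4 NCS and 4 CS at both times fits 0 to 4 eyes that moved from NCS to CS.

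**4. Effort by hand for colour vision.** The schedule has 17 colour assessments from Day 1 to Day 505, so 24 × 17 = 408 patient-visits for 24 randomised patients. Through Week 37 it has 10, so 24 × 10 = 240. Both are upper bounds, given the 7 to 13 doses, non-reconsent and early termination described in the SAP.

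**5. Precision of the added counts.** Exact two-sided 95% intervals for 0, 1 and 2 of 8 worsened are 0 to 36.9%, 0.3 to 52.7% and 3.2 to 65.1%. The added output would be descriptive only.

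**The case against.** The case for leaving the plan alone has several parts.

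- **Protocol 9.2.5 does not ask for shift tables.** It promises listings and summaries of ophthalmic assessments and names change from Baseline only for laboratory and vital-sign results. For abnormal ECGs it plans counts by time point, the same format as here. Its list of measures that are only listed is open-ended. A reader might infer a protocol breach; the wording does not support that.
- **By-visit counts are the SAP's usual format for graded data.** Physical examination grades (12.8) are handled the same way and are also named in the endpoint, while ECG grades (12.11) are only listed. This stands for the three graded eye tests. It does not explain Ishihara, which is numeric.
- **Much is already covered.** Listings show arm and visit and can be read at 8 patients per arm. The ocular TEAE summary counts patients with new or clinically worsened events. But protocol 10.3.1 keeps changes consistent with TED progression out of adverse events unless they are more severe than expected, so that route depends on investigator judgement. A reader might infer that worsening cannot be seen at all; that goes too far.
- **A worst-grade count has its own bias.** Patients followed longer have more chances to show an abnormal grade, and follow-up varies here. This stands, and it is why the fix needs a fixed window.
- **SAP Section 18, where final tables are named, is not in the supplied text.** A shift table there cannot be ruled out.

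A reader might also infer that all four tests are plainly part of the change-from-Baseline endpoint, or that the loss can be expressed as an incidence over all visits. The schedule and protocol 8.2 support the first clearly only for slit lamp. The second would need prevalence and persistence figures that the documents do not give.

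**Conclusion.** The point holds as a low-severity, low-cost improvement in reporting; no data are missing. It is firmest in two places: slit lamp, which is clearly in the endpoint but has no within-eye comparison, and Ishihara, the one numeric safety measure with no change summary. For visual field and fundus it rests on the broader reading of ophthalmic assessments and on the protocol 8.2.1 interest in new field defects.

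The size depends on how many eyes are abnormal at Baseline, which the documents do not give: no loss at a visit if none are, and an uncertainty of 0 to 2 newly abnormal eyes in an arm of 8 if two are abnormal at both times. The conclusion is limited to SAP Section 12 as supplied.

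**What to change.** - **SAP 12.4.** Add a by-arm, by-visit summary of change from Baseline in the proportion of plates correct (plates correct divided by plates shown), for each eye if recorded separately; 12.4 does not say. Add a count of patients who worsen by a stated margin. Set the margin before database lock by staff who are still masked: SAP Section 16 says the sponsor's clinical team was unmasked, while investigators, CRO clinical operations and CRO statisticians were not.
- **SAP 12.5 (by structure), 12.3 and 12.7 (by structure).** Add a shift table by eye and arm, from Baseline grade to worst post-baseline grade through a fixed common time point. Week 37 suits slit lamp and field. For fundus use the Week 29 examination, the only one after Baseline before Week 73. Use the number of patients assessed as denominator.
- **If SAP Section 18 already names such tables,** a cross-reference from Section 12 is enough.

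**Cost.** SAP wording and about four extra tables from data already collected, with no effect on sample size, power or alpha. Per arm, the three shift tables hold 7 × 2 × 9 = 126 cells (slit lamp), 2 × 9 = 18 (field) and 5 × 2 × 9 = 90 (fundus), 234 in total. The planned by-visit tables on the full schedule hold 7 × 2 × 17 × 3 = 714, 2 × 8 × 3 = 48 and 5 × 2 × 3 × 3 = 90, 852 in total, so the addition is about 27% (234 / 852). Most cells will be empty or near empty. Worst-grade counts will still depend on how many visits each patient attends inside the window, because SAP 6.2 does not impute safety results.
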